The anti-dementia drugs currently on the market (acetylcholinesterase inhibitors (ChEI) and memantine) do not have any documented disease-modifying effect in relation to the pathophysiology of AD as such, but only a symptomatic effect. When ChEI were introduced, analyzes of the optimal dosage level were carried out both in relation to safety and side effects, but also in relation to clinical efficacy. It appears from the early studies of the drug Donepezil that it was estimated that 80% would achieve optimal therapeutic serum levels at the standard dosage of 10 mg per day (3,4,5). Correspondingly, a dose-response relationship was found for the other ChEIs (rivastigmine, galantamine) and the partial glutamate receptor antagonist memantine (Ebixa), which is reserved for patients with moderate to severe AD or LBD, and a recommended dosage was established with a view to optimal clinical response (6). The indicative serum ranges are 80-200 nmol/l and 500-840 nmol/l for donepezil and memantine respectively (7). There have been remarkably few following studies investigating whether serum concentrations in a clinical setting are actually within the therapeutic reference ranges of the current recommendations. A recently published study suggests that very few patients in fact do reach a serum concentration within the recommended therapeutic reference ranges on the standard dosage (8). At the same time, few researchers have previously taken an interest in whether the occurrence of early side effects, possibly on a low dosage, and/or clinical need for repeated adjustments in drug dosing or alternatively change of preparation, could be due to abnormally high serum concentrations of the drug. Possibly reason for this could be genetic variation, sex differences, co-morbidity, compliance problems or drug interactions (9,10). For the planned research study conducted according to this protocol, we will initially focus on the two most widely used anti-dementia drugs, Donepezil and

Memantine, because an estimated 80% of patients who are treated with anti-dementia drugs are on one of these 2 drugs.

A pilot study carried out in collaboration between RVD and [The Laboratory of] Filadelfia showed that out of 24 blood samples, all taken from patients treated with donepezil at steady-state, only 8 samples, i.e. corresponding to 1/3, were within in the recommended therapeutic reference range. Ten samples were below the lower recommended limit, while 6 samples were above.

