tests, partly for serum concentration determination. They are also informed that they will receive at least 1 year of follow-up in RVD, against the usual ½ year. At the visit after 1 year, the same clinical tests and scales are carried out as during the patients' preliminary examination, and matters relating to compliance are queried. The other group (intervention group) will have an extra blood sample taken if they experience side effects from the treatment within the first 2 months. Everyone also has one extra blood test at each The ½- and 1-year check-ups. In addition, they will also be followed for at least 1 year against the normal ½ year. At the 1-year check-up, the same clinical tests and scales are carried out as in the pre-examination, and matters relating to compliance are queried. Subsequently, the respective compliance, distribution of serum concentrations, as well as the importance of serum concentration determination and derived dose regulation for the overall clinical response after 1 year (assessed on MMSE, ACE, NPI, DAD and CGI). A comparison is made of the occurrence, duration and outcome of side effects in the 2 groups, including the proportion of patients who had to change preparations or abandon medical treatment due to side effects. The project manager (alternatively the person performing the test) is blinded in relation to which group the patient is randomized to and to the result of serum values. The final statistical analysis of the clinical value of serum determinations and derivative monitoring is performed by an independent statistician. No participants will receive any form of remuneration for participation in the project. Any additional costs for transport are covered according to the appendix. Use of journal information Journal information is used to identify the target group, including clarifying inclusion and exclusion criteria (see these). During the project period of one year, the journal is used to document and monitor any side effects or unintended events, just as all possible side effects or unwanted events are entered into the patient's CRF.

FLOWCHART FOR PROJECT "MONANTI"

Inclusion criteria for participants

- All patients [evaluated at RVD] who after diagnostic assessment has been completed, meet the criteria for
- Alzheimer's Dementia (AD), (NIA-AA, (1)), Dementia with Lewy-Bodies (DLB) (15) or Parkinson's Disease Dementia (PDD) (18), and
- who are scheduled for treated with Donepezil or Memantine and

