As by custom in ordinary clinical practice [in RVD], all patients and relatives are informed about potential side effects at the start of treatment and dose adjustments. Side effects are routinely reported to the contact nurse by telephone, in practice this happens on the same day or within a few days after side effects occur. In connection with the project, participants in the intervention group will receive the same information about side effects as in routine clinical practice, supplemented by corresponding information about the need to report by telephone to the contact nurse in the event of side effects. Furthermore, all participants are asked about side effects at the ½-year and 1-year follow-up visits. In each individual case, an assessment will be made by one of the clinic's specialists (senior physicians) as to whether side effects should lead to dose reduction or discontinuation. All reported side effects are entered into the participant's CRF. As by clinical routine, all participants and relatives will be encouraged to contact the contact nurse by telephone in case of any suspicion of side effects. If the reported side effects are deemed to be related to the medicine, common practice is to either switch to an alternative anti-dementia drug or reduce the dose. It depends on a medical assessment whether there is a basis for changing the preparation or reducing the dose. In all such cases, in connection with the project, a blood test will be offered to determine the serum concentration. Common side effects (in 1-10% of subjects): Less than 5% of patients who have a blood test will develop a minor hematoma at the insertion site [of the needle]. This side effect is benign and will disappear without any treatment. Slight pain at the injection site itself and subsequent mild soreness may occur. It may occur that participants who are uptitrated in dose on the basis of low serum concentrations will develop side effects. These are mainly mild gastrointestinal side effects, and in rare cases cardiac side effects. Occurrence

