of such potential side effects will be closely monitored and the clinic will immediately respond accordingly. Apart from the time consumption of the cognitive tests and interviews, there are no other known side effects of these studies. There are no side effects or significant risks when recording standard EEG with modified photo-block. The participants can at any time during the EEG recording refuse to complete this study, which must then be complied with by the person in charge of the experiment. In this context, an adverse event (AE) is defined as: any adverse event in a patient or subject in a clinical trial after treatment with a medicinal product, without necessarily having a connection between this treatment and the adverse event.

Registration of unwanted events

All of the following information is recorded by the physician in charge of the study for each adverse event:

- Complete description of the unwanted event.
- Date and time of onset.
- Date and time of resolution.
- The severity of the incident must be assessed by the physician responsible for the study [primary investigator] according to the definitions below.
- Whether or not it is a serious incident.
- Whether the incident was expected or not.
- The relationship to the procedure, which must be assessed by the physician responsible for the study according to the definitions below.
- Action taken (if applicable).
- Result and information for all further follow-ups. Definitions of adverse event severity.

The following are the only definitions used to describe the severity of adverse events:

- Mild – The adverse event does not interfere with the subject's daily routine. It causes slight discomfort.
- Moderate – The adverse event interferes with some aspects of the subject's daily routine.
- Severe – The adverse event causes an inability to perform the subject's daily routine. Only one definition of severity is used for each adverse event (eg a statement such as "mild/moderate" is not acceptable). Moderate or serious adverse events are considered very unlikely in the present project.

Serious adverse events

A serious adverse event (SAE) is understood in this context as all medical occurrences, such as:

- results in death,
- is life-threatening,
- requires hospitalization or extension of an existing hospital stay, results in permanent or significant disability, or inability to work.

Adverse events that meet all of the following criteria:

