The study is intended to be conducted as a prospective single-blind randomized controlled study with a follow-up period of one year. This means that the professional who carries out tests and assessment of clinical effect as well as registration of the occurrence of side effects is unaware of whether the patient is in the control or intervention group.

Side effects

Common side effects (in 1-10% of the test subjects): A small proportion of the patients who have their dose increased on the basis of the blood concentration determination will be able to develop side effects, mainly from the gastrointestinal tract in the form of nausea, abdominal pain or loose stools. Mild headache and dizziness may also occur. The side effects are benign and will disappear after dose reduction without any treatment. Uncommon side effects (in 0.1-1% of participants): supposedly less than 1% may have transient cardiac side effects after increasing the dose based on the blood concentration measurement, typically problems associated with bradycardia (dizziness, fatigue, general malaise). These inconveniences are generally of a completely benign nature, and disappear quickly when the dose is reduced. Rare side effects (in 0.01-0.1% of participants) and very rare side effects (in less than 0.01% of participants): Transient liver effects, muscle cramps, heart block and muscle stiffness are seen in rare cases. Likewise, these side effects are generally reversible upon dose reduction.

Ethical considerations

The study will follow the Helsinki declaration of 1984, which was modified at the 41st World Congress in Hong Kong 1989. The study is approved by the Regional Scientific Ethics Committee for Region Zealand and the Data Protection Authority (we assess that the study is covered by Region Zealand's umbrella approval from the Data Protection Authority, and the study has been registered accordingly). Participants will only be included after full written and oral information and written informed consent. The participants can withdraw

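### Side-effect duration and outcome are compared between arms with no stated denominator; by default only affected participants are compared, a group that the allocated arm itself changes

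*Combined protocol and SAP*

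**What the plan says.** The comparison is set out in the Recruitment section: "A comparison is made of the occurrence, duration and outcome of side effects in the 2 groups". The same sentence adds "the proportion of patients who had to change preparations or abandon medical treatment due to side effects". Neither that section nor Statistics and power calculation states an analysis set for duration and outcome, a value for participants without a side effect, or a rule for events still ongoing at 1 year.

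Registration of unwanted events lists the items recorded for each adverse event, among them the onset date and "Date and time of resolution".

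Three further places bear on who becomes affected:

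- Study execution and visits gives the intervention group a serum test for early side effects and another at the half-year visit, each with dose adjustment. The control group has only a single blood test at the end, apart from the genetic sample that everyone gives.
- Side Effects and Adverse Events accepts a consequence of this: "It may occur that participants who are uptitrated in dose on the basis of low serum concentrations will develop side effects". It calls these effects mainly mild and gastrointestinal. The lay summary puts them in its 1-10% frequency class and says: "The side effects are benign and will disappear after dose reduction without any treatment".
- Side Effects and Adverse Events also gives the intervention group supplementary information on the need to report side effects by telephone.

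**The concern.** Duration and outcome are undefined for a participant with no side effect. If they are compared only where they exist, the comparison conditions on an event that happens after randomisation and that the allocated strategy influences. The affected participants in the two arms are then different kinds of patients with different kinds of events.

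If serum guidance adds short, mild, reversible events, they pull down the intervention arm's average duration and push up its share resolved, although no participant has done better. A report could then credit serum monitoring with shorter side effects while total time with side effects rose. Reducing side effects is part of the case for monitoring in the lay summary, so the result would be used.

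**Working it through.** **No figure to reproduce.** The documents give no side-effect rate or duration by arm. The planned 55 per arm (7.84 × 0.4375 / 0.0625 = 54.88, rounded up) is used here only to turn shares into counts.

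**Inputs from the documents**

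- Share that might be up-titrated: in the donepezil pilot (Background), "Ten samples were below the lower recommended limit, while 6 samples were above", out of 24. So 10/24 = 42% were below range.
- Frequency of added side effects: 1-10% (lay summary). The text can be read as applying to those up-titrated or to participants generally, so both are shown.

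**Assumed inputs**

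- p = 20% of controls affected, mean d1 = 30 days.
- The intervention arm has the same base events plus an added share q with mean d2 = 7 days.
- Ranges: p from 10% to 30%, d2 of 7 or 14 days.

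**Formulas**

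- Mean duration among the affected, intervention arm: (p·d1 + q·d2) / (p + q). Control arm: d1.
- Burden per randomised participant, intervention arm: p·d1 + q·d2. Control arm: p·d1 = 0.20 × 30 = 6.00 days.

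**Results at p = 20%, d1 = 30, d2 = 7**

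| Added share q | Extra affected of 55 | Mean duration among affected (control 30 days) | Burden per participant (control 6.00 days) |
|---|---|---|---|
| 1% of 42% = 0.42% | 0.2 | 29.5 | 6.03 (+0.5%) |
| 10% of 42% = 4.17% | 2.3 | (6.00 + 0.29) / 0.2417 = 26.0 | 6.29 (+4.9%) |
| 10% of the arm | 5.5 | (6.00 + 0.70) / 0.30 = 22.3 | 6.70 (+11.7%) |

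**Over the assumed ranges**

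- q = 0.42%: duration 0.2 to 0.9 days shorter, burden 0.3% to 1.9% higher.
- q = 4.17%: 2.0 to 6.8 days shorter, burden 3% to 19% higher.
- q = 10%: 4.0 to 11.5 days shorter, burden 8% to 47% higher.

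The two summaries point in opposite directions whenever d2 < d1 and base events are unchanged.

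**Outcome.** Let u be the unresolved share of base events, and suppose all added events resolve. Among the affected, the unresolved share falls from u to u·p/(p + q). At p = 20% and q = 10% this is 0.20/0.30, or two thirds of u. Over all randomised participants it stays at p·u in both arms.

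**If early serum testing truly shortens base events by s days.** Burden is unchanged when s = q·d2/p. That is 0.0417 × 7 / 0.20 = 1.5 days, or 0.10 × 7 / 0.20 = 3.5 days at q = 10%. In the second case burden is 0.20 × 26.5 + 0.70 = 6.0 days, equal to control. Mean duration among the affected is then 6.0/0.30 = 20.0 v 30 days. A true shortening of 3.5 days would read as 10 days, because dilution and benefit are mixed.

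**The case against.** The restriction to affected participants is not written. The plan says only that the two groups are compared, and it announces no test of duration. A reader might infer that a conditional analysis has been chosen; the documents support only that the denominator is missing and that per-event recording makes this the default.

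The same sentence also compares occurrence and the proportion changing or stopping treatment, both of which can be taken over whole arms. A rise in affected participants would therefore be visible beside a shorter duration. That limits the harm, but it does not repair the duration and outcome comparisons, which are listed in their own right.

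The size may be small, and the direction is not settled. The documents call the added effects mild and reversible but give no days, and rare cardiac effects are mentioned too. Early serum testing could genuinely shorten side effects. The reporting route is also weaker than it first looks: the section on side effects encourages all participants to telephone and asks all of them about side effects at both follow-up visits.

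Finally, a reader might treat this as a headline result because side effects appear in the title. The title names their incidence. Duration and outcome of side effects are not in the aims, the hypotheses or the list of outcome variables.

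**Conclusion.** The point holds as a weakness of method. Followed as written, the duration and outcome comparisons fall by default on a post-randomisation group whose membership the arm changes, so randomisation does not protect them. This does not depend on how large the distortion is.

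The size rests on assumptions. With 20% of controls affected for 30 days and added events of 7 days, the apparent shortening is 4.0 days with burden 5% higher (q = 4.2%), or 7.7 days with burden 12% higher (q = 10%). At 1% of those below range it is negligible. If added events were as long as base events, mean duration would not be distorted; if longer, the distortion would run the other way.

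It does not follow that serum guidance will look better while doing harm. A true shortening could offset or reverse the added burden. The defect is that duration among the affected cannot tell these cases apart. The change is worth making; the sample size is unaffected.

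**What to change.** Add the following to the analysis plan before allocation is revealed:

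1. **Duration.** For every randomised participant, count days with any side effect up to 1 year: zero if none, overlapping events counted once, ongoing events counted to 1 year. Compare arm means with a bootstrap 95% confidence interval. State which adverse-event records count as side effects.
2. **Outcome.** Compare the proportion of all randomised participants with a side effect that is unresolved at 1 year or that led to change or stopping of treatment.
3. **Withdrawals.** State a rule for participants who leave before 1 year. Withdrawal criteria for all includes a switch to a drug not measured in the study, and side effects can prompt a switch, so this missingness is informative. One option is to count days to last contact, treat withdrawal due to side effects as an unfavourable outcome, and add a sensitivity analysis.
4. **Duration among the affected.** Report by arm as description only.
5. **Reporting.** Note the different reporting instructions in the two arms as a limitation; a whole-arm denominator does not remove it.

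Onset and resolution dates are already collected. The cost is a little more analysis work and an explicit assumption about withdrawn participants.

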- who give informed consent to participation.

Both patients with mild-moderate dementia and patients with moderate to severe dementia are enrolled, because we want to explore whether the correlation between effect and serum concentration varies depending on the stage of dementia.

Exclusion criteria for participants

- Patients not accompanied by relatives to study visits.
- Patients who live alone and do not have help with the medication administration
- Inability to cooperate to testing, also severely impaired vision or hearing, amputation or other severe disabilities.
- Inability to meaningfully give informed consent due to cognitive impairment.
- Patients with known underlying psychiatric illnesses (schizophrenia, bipolar affective disorder, etc.). Depression is permitted if the patient has been on regular medical treatment for at least 3 months prior to inclusion.
- Patients with known neurological conditions (MS, epilepsy, brain tumors etc.), which in themselves could be contributing to the patients cognitive symptoms.
- Patients with medical conditions (kidney, liver, metabolic etc.) which in themselves could be contributing to the patients cognitive symptoms.
- Patients who, currently or in the past 3 months before enrollment, have been treated with anti-psychotics or neuroleptics. Minimal doses of benzodiazepines or hypnotics are accepted.
- Patients with previous heavy abuse of alcohol or illegal drugs, or any abuse within the last 3 months before inclusion.

- Patients with previous severe head trauma or neuroinfections, which in themselves could contribute to the patients cognitive symptoms.
- Patients who have had ECT [Electro Convulsive Therapy] treatment within the last 3 months.
- General anesthesia within the last 3 months.

Withdrawal criteria for all

- The participant or relative wishes to withdraw from the study.
- Symptoms deemed unacceptable by the physician responsible for the trial in accordance with the above exclusion criteria.
- Medical reasons, including if the treatment is changed to an anti-dementia drug for which serum concentrations are not measured in this study [galantamin or rivastigmine].

Study execution and visits

Inclusion interview/recruitment

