- Approx. 30 patients will have a standard EEG with modified photo-block performed, if Donepezil treatment has not been started beforehand. These approx. 30 patients will have another standard EEG performed with the same modified photo-block approx. one year later in connection with the point below.
- After one year, all participants are called for one additional visit. Here, a blood test is carried out on all participants, just as all participants are offered a dosage adjustment depending on the serum concentration, also if appropriate a change of preparation. The same clinical tests are carried out as during the preliminary examination [or enrollment visit]. All participants are asked about treatment compliance.

- If there is a need for dose adjustment or possibly prescription change during the project, the decision will be made by the person in charge of the experiment [primary investigator] and not the project manager (PhD student). Practical handling is carried out in collaboration between the project manager and the project nurse.
- A blinded calculation of the distribution of serum concentration, clinical scores, compliance and occurrence of side effects [is done by a statistician not affiliated with the study]

Study visits

- In connection with the information interview, as part of the general clinical course, the initial information about the project is provided and project information is provided.
- Potential participants are contacted to participate in one extra visit (inclusion interview with project manager) together with the relative.
- If informed consent is obtained, one extra visit to the clinic 1 year after enrollment ["1 year follow-up visit"]. The visit ½ year after enrollment is part of the routine follow-up at RVD.

End of study

The study is ended on the date when the last participant (cf. power calculation) has been evaluated at the 1-year follow-up visit. Subsequently, after registration and [external] monitoring [of data quality], data will be transferred to blinded statistical analysis by a statistician. A need for future follow-up visits will be conducted at the GPs office.

Study design

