The Study will be conducted in accordance with the Helsinki Declaration of 1984, modified at the 41st World Congress in Hong Kong 1989. The study has been approved by the local Scientific Ethics Committee (SJ-596) and the Danish Data Protection Agency. Participants will only be included after full written and verbal information and provision of informed written consent. Participants can withdraw from the study at any time without reason, and without this affecting any future treatment. Only participants who are deemed to be able to understand the information and independently consent to study participation are included. This also applies to patients with moderate to severe dementia. It may happen that, in connection with the blood sampling and dose regulation (up-adjustment), inappropriate side effects appear temporarily, mainly in the form of gastro-intestinal discomfort (indigestion, abdominal pain, loose stools) and heart rhythm disturbances. Should this occur, the project manager will arrange for an immediate dose reduction and, if cardiac problems are suspected, for an emergency ECG to be taken. Depending on the nature and severity of the

discomfort, an appropriate medical response is given. It may also happen that a participant in the intervention group shows signs of unusual worsening of their dementia at the ½ or 1-year visit. Here, it is the responsibility of the project manager to screen the patient for co-morbidity (possibly in collaboration with his or her GP), and to ensure that the participant is offered combination treatment (AchE inhibitor + Memantine), especially if the S-value of the current treatment is at the recommended level. The participant continues regardless of this in the protocol (if it occurs at the ½-year visit), unless he or she express a wish to withdraw from the study. In addition to determining serum concentrations, the blood samples are used for genetic analysis of variants of liver enzymes [cyp2D6], APOE and BchE-K/K. Participants or relatives do not get specific feedback on the results of these analyses, which will only be used to assess the genetic variation in the population, as well as its significance in relation to the metabolism of anti-dementia drugs. It is our opinion that the expected disadvantages, discomfort and risks for study participants are small and do not outweigh the importance of the expected results.

Approval and monitoring by external authorities

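### Symptom-based withdrawal can follow from the decline the trial measures, is judged by an investigator not stated to be blinded, and comes with no plan for 12-month outcomes or analysis of those withdrawn

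*Combined protocol and SAP*

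**What the plan says.** Under *Withdrawal criteria for all* there are three routes out of the study: a wish of the participant or relative; "Symptoms deemed unacceptable by the physician responsible for the trial in accordance with the above exclusion criteria"; and "Medical reasons, including if the treatment is changed to an anti-dementia drug for which serum concentrations are not measured in this study". The second has no threshold and no timing. The exclusions it refers back to include "Inability to cooperate to testing, also severely impaired vision or hearing, amputation or other severe disabilities" and "Inability to meaningfully give informed consent due to cognitive impairment".

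The section on registering unwanted events equates the physician responsible for the study with the primary investigator. Under *Study execution and visits*, where a dose adjustment or prescription change is needed, "the decision will be made by the person in charge of the experiment", again glossed as the primary investigator and expressly not the project manager. Blinding is stated for the project manager, for the tester or rater, and for the statistical analysis (*Recruitment*, *Study design*, *Blinding*, *End of study*). The primary investigator is not among them.

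*Ethical considerations* takes the case where a "participant in the intervention group shows signs of unusual worsening of their dementia" at the half-year or one-year visit. It describes screening for comorbidity and an offer of combination treatment, and then says: "The participant continues regardless of this in the protocol (if it occurs at the ½-year visit"), unless the participant wishes to leave. There is no matching sentence for controls.

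The sample size rests on a responder outcome, an MMSE fall of less than 2 points in one year, with 55 participants per group and 110 in total. The available text names no analysis population, no method for missing outcomes, no assessment after withdrawal and no dropout allowance.

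**The concern.** An entry criterion describes who is suitable at the start. Used as a reason for withdrawal during a one-year dementia trial, it can act on the outcome itself: a participant who loses the ability to be tested or to consent has probably declined, and is likely to be a non-responder on the MMSE definition. Removing that person raises the observed success rate of the arm he or she leaves.

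If both arms lost non-responders in the same proportion, the distortion would be modest. The design does not secure that. The criterion is discretionary, and the person applying it also decides dose changes and is not stated to be blinded. The only sentence that tells staff to keep a worsening participant in the study mentions one arm. Since nothing provides for a 12-month outcome after withdrawal, and no analysis set brings withdrawn participants back into the comparison, any imbalance goes straight into the result.

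**Working it through.** **Plan's own figure.** Inputs from *Statistics and power calculation*: P1 = 0.50, P2 = 0.75, two-sided 5% (1.96), power 80% (0.84).

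N = (1.96 + 0.84)² × (0.50 × 0.50 + 0.75 × 0.25) / 0.25² = 7.84 × 0.4375 / 0.0625 = 54.88, rounded up to 55 per arm. The total of 110 is exactly 2 × 55, so it contains no allowance for loss. Power at 55 per arm by the same unpooled normal approximation is 80.0%. The figure reproduces and does not depend on the withdrawal rule.

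**Model for selective loss.** Let w be the share of an arm's non-responders who are withdrawn and leave the analysis. No responders are assumed lost. The documents give no value for w; 10%, 20% and 30% are assumptions.

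- Observed rate = p / (p + (1 − p)(1 − w))
- Remaining n = 55 × (p + (1 − p)(1 − w))
- Power = Φ(d / SE − 1.96), where d is the observed difference and SE = √(p₁(1 − p₁)/n₁ + p₂(1 − p₂)/n₂), using the observed rates and remaining numbers

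Control expects 27.5 responders and 27.5 non-responders, so w of 10%, 20% and 30% removes 2.75, 5.5 and 8.25 people. Intervention expects 41.25 and 13.75, so the same shares remove 1.375, 2.75 and 4.125.

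Example, control only, w = 10%: rate = 27.5 / (27.5 + 24.75) = 27.5 / 52.25 = 52.6%; difference = 75 − 52.6 = 22.4 points; SE = √(0.526 × 0.474 / 52.25 + 0.75 × 0.25 / 55) = 0.0904; power = Φ(0.2237 / 0.0904 − 1.96) = 69.6%.

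| w | Control only: rate, difference, power | Both arms: rates, difference, power | Intervention only: rate, difference |
|---|---|---|---|
| 0% | 50.0%, 25.0, 80.0% | 50.0% / 75.0%, 25.0, 80.0% | 75.0%, 25.0 |
| 10% | 52.6%, 22.4, 69.6% | 52.6% / 76.9%, 24.3, 77.1% | 76.9%, 26.9 |
| 20% | 55.6%, 19.4, 56.4% | 55.6% / 78.9%, 23.4, 73.5% | 78.9%, 28.9 |
| 30% | 58.8%, 16.2, 41.5% | 58.8% / 81.1%, 22.3, 69.1% | 81.1%, 31.1 |

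**No true effect (50% in both arms).** Control-only loss at 10%, 20% and 30% gives apparent differences of −2.6, −5.6 and −8.8 points, and two-sided rejection rates of 5.9%, 8.8% and 14.6% in place of 5%, mostly in favour of control.

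The larger distortion comes from imbalance between the arms; equal proportional loss costs much less.

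**The case against.** A reader might infer something stronger: that worsening controls leave while equally worse intervention participants must stay, so that the trial is biased against serum guidance. The documents do not support this.

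- The withdrawal criteria apply to everyone, so all three routes remain open to the intervention arm.
- The continuation sentence covers only worsening found at the half-year visit, keeps the participant's own right to leave, and does not say that it overrides the withdrawal criteria.
- Read in place, it most naturally refers back to the sentence before it: comorbidity screening and an offer of combination treatment do not end participation. It may name only the intervention arm because that sentence refers to a serum value at follow-up.
- Nothing sends worsening controls out of the study.
- The direction could be the reverse. Serum-guided drug changes in the intervention arm could lead to more withdrawals there through the drug-switch criterion.

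It is also fair to say that much of the exclusion list concerns history or other illness, and that moderate to severe dementia is admitted at entry, so progression alone does not meet the list. The losses in the calculation are assumed, and a participant who cannot be tested has no MMSE whatever the withdrawal rule says. Nor are dose decisions solely the primary investigator's: *Side Effects and Adverse Events* gives some to the clinic's senior physicians, and *Ethical considerations* has the project manager arrange dose reductions. Those passages must be reconciled with *Study execution and visits* and *Blinding*.

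These points rule out a stated differential rule and a known direction of bias. They leave the core standing: two exclusions that progression can reach, no threshold, a decision-maker not stated to be blinded, continuation wording for one arm only, and no handling of the lost outcomes. That untestable participants lack an MMSE under any rule is itself a reason to state how they are scored.

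**Conclusion.** The concern holds as a gap in the plan. Followed as written, the plan permits outcome-related and possibly differential loss from the 12-month comparison, and contains nothing that would recover the lost outcomes or limit the effect on the analysis. Neither the direction nor the size can be read from the documents.

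The scale is conditional on two assumptions: that 10-30% of non-responders are withdrawn, and that no responder is. On those terms the effect on the planned 25-point difference runs from slight (24.3 points, equal 10% loss in both arms) to serious (16.2 points with about 42% power, 30% loss from control only), with inflation to as much as 31.1 points if the loss falls on the intervention arm. Because the direction is unknown, it cannot be corrected after the fact by a simple adjustment.

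**What to change.** 1. Reconcile the symptom criterion under *Withdrawal criteria for all* with the continuation sentence in *Ethical considerations*, so that one study-withdrawal rule applies to both arms.
2. Separate study follow-up from clinical decisions. State that meeting the symptom criterion does not by itself end follow-up: the 12-month assessment is still sought in both arms unless consent is withdrawn or continued participation is not ethically permitted. Clinical decisions stay with the treating physicians.
3. Analyse all randomised participants in the arm to which they were allocated.
4. Count a participant whom the blinded rater records as untestable at 12 months because of dementia severity as not having optimized clinical effect, in both arms alike. Having the blinded rater record this keeps the judgement away from whoever decides doses.
5. Prespecify a sensitivity analysis for outcomes missing for other reasons, and report withdrawals by arm and by criterion.

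The cost is a few sentences and no extra visits beyond the 12-month one already planned. Some outcomes would be assigned by rule instead of by a completed MMSE. At version 1.9 (April 2022) recruitment had closed and participants enrolled from February 2020 could already have finished; for them only the analysis rule can apply. The last participant was not expected to finish until March 2023, so the analysis rules could still be fixed before unblinding.
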